## 1.0 BACKGROUND AND RATIONALE

#### 1.1 Study Synopsis

This is a single arm, non-randomized study of 25 adult subjects with suspected kidney cancer and planned surgical nephrectomy that will undergo a contrast enhanced ultrasound (CEUS) of the kidneys to predict kidney mass histologic diagnosis, subtype and stage.

#### 1.2 Kidney Cancer

Kidney cancer incidence has more than doubled over the past 2 decades with nearly 70,000 new cases projected for 2019[1, 2]. This exponential growth is attributable largely to increased detection of incidental small kidney masses[3, 4]. Most of these small masses are resected; however, only 20% harbor aggressive disease. The remaining 80% consist of benign tumors or non-aggressive cancers[5-7] that may not need resection. Unfortunately, current diagnostic techniques do not reliably differentiate aggressive from non-aggressive subtypes. Identifying non-aggressive subtypes pre-resection would reduce unnecessary surgeries and associated risks including kidney function loss, a risk particularly high among individuals with chronic kidney disease (CKD).

Contrast-enhanced computed tomography (CT) or magnetic resonance imaging (MRI) are the standard tests to diagnose kidney cancer and guide management. However, CT and MRI have key disadvantages that limit their ability to precisely diagnose and stage kidney cancer resulting in costly surgeries and their associated morbidities in patients that may not have needed resection. First, both modalities capture image snapshots over time, and important enhancement characteristics may be missed if the snapshot is not timed correctly. Second, contrast extravasation leads to decreased sensitivity to vascular enhancement, limiting their staging ability. Third, CT and MRI are contraindicated among individuals with moderate and severe CKD, contrast allergies and/or metal implants, relegating these patients to substandard diagnostics. Ultrasound (US) is a safe, inexpensive and accessible imaging tool often used in patients with CKD, but it suffers from a lack of sensitivity. Given the rising incidence of kidney cancer and the increasing number of individuals with CKD who cannot undergo CT/MRI, there is an urgent and unmet need to identify imaging that can safely and accurately differentiate kidney masses needing resection from those that do not. Moreover, among all individuals with kidney masses, including those without CT/MRI contraindications, there is a clear and unmet need to identify imaging that can accurately diagnose subtype and characterize vascular involvement, a key factor in cancer staging.

We propose to investigate an advanced contrast-enhanced ultrasound (CEUS) technique as a novel imaging tool to address these critical gaps in kidney mass diagnosis and staging. We will accomplish the following aims:

1) to predict histologic subtype and stage using 3D CEUS-generated metrics in humans and 2) to compare the predictive capabilities of 2 different CEUS imaging techniques (one using bolus and one using infusion injection) in humans.

#### 1.3 Kidney Cancer Histologic Subtypes

The majority of kidney cancers are renal cell carcinomas (RCC) of which there are three main subtypes: clear cell, papillary and chromophobe. The subtypes differ in incidence, prognosis[8, 9] and vascularity[10]. Accurate subtyping is critical to clinical decision-making as less aggressive subtypes do not require immediate resection. Differentiation of clear cell (a higher risk subtype requiring resection) from other subtypes or benign kidney masses has the potential to reduce unnecessary surgeries[6]. CT/MRI, the predominant imaging modalities used to diagnose RCC, do not reliably predict cancer subtype or grade. Other than surgical resection, biopsy is the only reliable way to preoperatively determine histologic subtype and tumor grade. However, biopsy is not performed at all centers[11] and is subject to sampling error, with as many as 20% of biopsies being non-diagnostic[12].

Differences in tissue vascularity cause differing tissue enhancement[13]. CEUS is highly sensitive for tissue enhancement which can be leveraged to differentiate kidney mass subtype based on enhancement properties. Previous studies have reported accurate diagnosis[14] and subtyping[15] of kidney masses using single plane CEUS with qualitative interpretations. 3D CEUS-generated metrics will capture enhancement in multiple planes and thus produce a more complete picture of the entire mass. Specifically, we will use 3D CEUS-generated quantitative metrics to characterize mass vascularity.

#### 1.4 Tumor staging

For malignant masses requiring resection, treatment decisions are often based on CT/MRI-derived staging. Tumors confined to the kidney are stage 1 or 2. Vascular involvement classifies a tumor as stage 3 or higher. However, CT/MRI often miss subtle vascular involvement, leaving such involvement undetected until pathologic inspection post-resection, making preoperative prognosis estimation inaccurate. Stages 1, 2 and 3 have very different survival rates (81%, 74% and 53%[1], respectively), rendering accurate preoperative staging essential for surgical planning and patient counseling. 3D CEUS' vascular enhancement sensitivity and real-time imaging may better characterize small vessel involvement, aiding surgical planning and patient counseling. In addition, 3D volume rendering of the vessels may be useful for vasculature-based mass staging.

#### 1.5 Chronic Kidney Disease

Individuals with advanced CKD and a kidney mass offer a unique challenge. These patients have an increased risk of kidney cancer, and risk rises with CKD severity[16]. As CKD severity worsens, contrast CT/MRI risks also increase. If such patients undergo contrast CT, they risk kidney function loss and potential progression to end-stage kidney disease. If they undergo contrast MRI, they risk development of a rare but devastating disease, nephrogenic sclerosing fibrosis. However, without such imaging, they either risk missed detection of a mass needing resection or undergo preemptive resection, potentially of a mass not needing resection and resulting in further loss of kidney function. Identification of a contrast imaging tool that does not pose increased risks to patients with CKD would eliminate these unnecessary risks.

The advanced CEUS techniques of 3D imaging provides a powerful opportunity to fill existing gaps in kidney mass care, including subtype prediction and staging. Additionally, for those with advanced CKD and other contraindications to CT/MRI, CEUS allows for contrast imaging not possible with existing imaging options.

#### 1.6 Contrast Enhanced Ultrasound

CEUS has several features that distinguish it from contrast CT/MRI. Unlike contrast CT/MRI, CEUS captures real-time images, enabling dynamic visualization of contrast over time. In addition, the CEUS contrast agent, microbubbles, remains intravascular, and is thus sensitive to lesion enhancement and small vessel involvement, giving CEUS the potential to inform kidney mass staging and surgical planning, capabilities not currently possessed by CT/MRI.

In addition, CEUS microbubbles differ from CT/MRI contrast agents in that they are cleared by the lungs within minutes of administration and have no known nephrotoxicity, making CEUS safe for patients with advanced CKD. For these individuals, CEUS availability would mean access to contrastenhanced imaging, which would significantly improve the ability to provide a definitive mass diagnosis and increase the chance of avoiding unnecessary surgery. CEUS maintains the advantages of conventional US (lower cost in comparison to CT/MRI and safety).

To-date, most CEUS research has utilized a 2D approach. By adapting routine imaging techniques, we can generate three-dimensional (3D) CEUS images. Our preliminary work suggests that expanding 2D CEUS to a 3D technique will provide deeper data about mass enhancement, facilitating subtype differentiation. Moreover, our group has developed image analysis techniques that can generate 3D renderings of the vasculature (described below).

In 2D or 3D CEUS, microbubbles can be administered by bolus or continuous infusion dosing which correspond with low mechanical index (MI) and flash-replenishment imaging (F-R), respectively. The two approaches yield different information. The optimal approach is unknown.

With bolus administration of undiluted microbubbles, CEUS quantifies measurements like peak intensity, time to peak intensity, and wash-in/wash-out rates from the time intensity curve (TIC), each of which may be used to predict mass subtype. Alternatively, infusion of diluted microbubbles facilitates longer imaging times and uses faster frame rates. Longer imaging time allows for imaging in multiple planes which can capture multiple masses or different planes in a single mass, providing richer information. Faster frame rates can capture rapid wash-in rates with greater granularity than bolus dosing. However, the infusion method TIC does not quantify a wash-out rate, eliminating one metric that may contribute to subtype classification accuracy. Existing data suggest that bolus dosing 2D CEUS has comparable accuracy for malignancy detection compared to contrast-enhanced CT and MRI[17]. The accuracy of infusion dosing is unknown. We will adapt both approaches to generate 3D CEUS images.

### 1.7 Contrast-Enhanced Ultrasound Diagnostic Imaging of the Kidney

Ultrasound (US) imaging of the kidney is typically performed in the United States without contrast as no US contrast agent is currently approved for this indication. Without contrast, malignant tumors often cannot be definitively differentiated from benign tumors or pseudotumors. For this reason, following the identification of a kidney lesion via US without contrast, contrast-enhanced CT or MRI is then performed to stage and grade the lesion.

CEUS of the kidney for mass or lesion characterization is currently being performed in only certain centers in the United States and is more widespread outside the United States. US contrast agents are gas-filled microbubbles which are intravenously administered in very small volume boluses or slow infusions. These microbubbles typically have mean diameters between 1 to 6 µm, remain intravascular for several minutes, and do not diffuse into the interstitium (pure blood-pool agents)[18]. Three US contrast agents are Food and Drug Administration (FDA) approved for human use: perflutren lipid microspheres (Definity®), sulfur hexafluoride lipid microspheres and perflutren protein-type A microspheres (Optison®). All are FDA indicated for use in cardiac studies. The intent of this study is not to change the labeling of either FDA-approved agent.

#### 1.8 Contrast Agents

Definity® (perflutren lipid) is an FDA-approved US contrast agent indicated to opacify the left ventricular chamber and to improve the delineation of the left ventricular endocardial border in patients with sub-optimal echocardiograms. It is activated by mechanical agitation with a Vialmix® which produces a milky white injectable suspension of perflutren lipid microspheres composed of octafluoropropane. Activated perflutren may be injected by either an intravenous bolus or infusion. See

http://www.accessdata.fda.gov/scripts/cder/drugsatfda/ for full prescribing information. When used in this setting, the maximum dose of perflutren is administered as either bolus doses or one single intravenous infusion.

### 1.9 Associated Toxicities

Most safety studies have been performed in cardiac patients as this was the only FDA approved indication. Thus far, microbubble agents have been shown to be quite safe[19, 20]. In pre-market clinical trials, 1716 subjects were evaluated with activated perflutren lipid. Of the 1716 subjects, 144 (8.4%) had at least one treatment-related adverse reaction. There were 26 serious adverse events and 15 (0.9%) subjects discontinued because of an adverse event, 1 due to a hypersensitivity reaction and the rest due to dizziness, chest pain, dyspnea or back pain. The events appeared within 1 - 15 minutes of the drug administration and were of moderate intensity resolving usually without treatment within minutes or hours after onset. Of the 11 other serious adverse events, which appeared within 2-15 days of the drug administration, all appeared to be a progression of underlying cardiac and non-cardiac disease. Nineteen subjects (1.1%) suffered serious cardiopulmonary adverse events including 8 deaths. The deaths occurred several days after activated perflutren lipid administration and appear to be related to the course of underlying disease.

For all AEs, there were no differences in the overall incidence based on age, gender, or route of administration. The most common events were (% of patients experiencing): headache (2.3%), back and renal pain (1.2%), flushing (1.1%) and nausea (1.0%).

Initial post-marketing experience, which included over 1 million patients with 5 years surveillance, showed the only medically significant risk was rare allergic events, occurring at a rate of 1 in 10,000[20].

#### 1.10 Cardiopulmonary Reactions

Cardiopulmonary contraindications include cardiac shunts and hypersensitivity to perflutren. The initial mandated 30-minute monitoring period was limited to patients with pulmonary hypertension or unstable cardiopulmonary conditions. The mandatory 30-minute monitoring period was removed in 2011, although a statement remained that most serious cardiopulmonary reactions occur within 30 minutes of administration. For this reason, the label states that cardiopulmonary resuscitation personnel and equipment be readily available prior to perflutren administration, and that all patients be monitored for acute reactions.

Although recent studies have shown no increased risk in patients with pulmonary hypertension[21], patients with a history of known cardiac shunts, pulmonary hypertension or unstable cardiopulmonary conditions

will be excluded from our study. In addition, any patient with a suspected reaction during imaging will be monitored 30-minutes post-contrast agent administration by clinical or research nurse.

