#### 4.2.2 Imaging Procedures

#### 4.2.2.1 Low MI imaging with sweeps

Upon subject arrival, a urine pregnancy test will be conducted for subjects with child bearing potential. Once confirmed that a subject is eligible, a nurse will place an intravenous (IV) catheter, and a sonographer will determine mass location and approach with a baseline B-mode US. The nurse will prepare the CEUS contrast agent, Definity®, to be administered via infusion pump according to package insert instructions. We will use a Siemens ACUSON Sequoia S512 with a 4C1 curved array transducer equipped with cadence pulse sequencing technology for contrast-enhanced imaging.

Each subject will be injected with a bolus of 0.2-0.4 mL undiluted microbubbles placed on an infusion pump for consistent injection rate and followed by 5mL sterile saline. The sonographer will capture sweeps through the kidney in 2-3 different planes (i.e. x-y, y-z, or x-z) of imaging during contrast infusion. Each imaging plane will require a new bolus. During imaging, the subject will be instructed to take shallow breaths to minimize movement artifact. We will capture a B-mode image perpendicular to each sweep direction to determine the total length of each sweep. The subject will be instructed to take shallow breaths to minimize movement artifact. Imaging time will be 15-20 minutes.

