#### 4.2.2.2 Flash-replenishment infusion imaging

Following low MI bolus imaging, we will use the F-R infusion protocol and infuse diluted microbubbles with a calibrated syringe pump. We will translate the transducer across the mass in 0.5-1 cm steps to image the entire mass, executing a F-R pulse at each step. Imaging time will be 3-15 minutes depending on mass size. We will monitor the subject for adverse

reactions during the procedure. Images will be coded and stored for later analysis.

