#### 4.3 Time and Events Table

Consent can be obtained and signed at either screening visit or during the pre-study visit. It will always be reviewed at prestudy visit, even if signed during screening visit.

Comprehensive medical history obtained at time of enrollment; thereafter history focused on symptoms and assessments. Women of childbearing potential must have negative urine pregnancy test on the day of CEUS study, prior to the study. Adverse event assessment will happen during the CEUS study when they will be monitored by nursing staff with vital signs (blood pressure and heart rate) recorded in the hospital's electronic monitoring system. Adverse events will be recorded on an adverse events CRF.

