#### 5.3 Treatment Regimen

The contrast agent will be dosed undiluted (0.2-0.4 mL Definity) for up to 7 intravenous injections, depending on the number of lesions (2-3 bolus injections per lesion and one infusion injection). The activated undiluted dose will be placed in the tubing and attached to an infusion pump loaded with a syringe of sterile saline. The pump will be programmed to a standard rate for all patients and set to administer a total of 5 mL saline flush after the contrast agent is fully injected. Infusion dosing will be used after completion of bolus dosing.

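### The 30-minute nurse observation misses a reaction that starts after imaging, and routine observation has no stated end

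*Combined protocol and SAP*

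**What the plan says.** The plan's statements on observation after contrast are these:

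- **Section 1.10, the study's own rule:** "any patient with a suspected reaction during imaging will be monitored 30-minutes post-contrast agent administration by clinical or research nurse". This is the only post-contrast duration given for nurse observation, and it depends on symptoms seen during imaging.
- **Section 1.10, the label:** "The mandatory 30-minute monitoring period was removed in 2011, although a statement remained that most serious cardiopulmonary reactions occur within 30 minutes of administration". The same section says the former mandate applied only to patients with pulmonary hypertension or unstable cardiopulmonary disease. It reports that the label now asks that "all patients be monitored for acute reactions".
- **Section 1.9, onset in the pre-market trials:** "The events appeared within 1 - 15 minutes of the drug administration".
- **Section 4.2.2.2:** subjects are watched for adverse reactions while the procedure is under way.
- **Section 4.3, footnote 4:** "Adverse event assessment will happen during the CEUS study when they will be monitored by nursing staff with vital signs". No end time follows. The events table marks AE assessment at the CEUS study and at early termination, but not in the post-CEUS column.
- **Order and length of contrast:** "Infusion dosing will be used after completion of bolus dosing" (Section 5.3). For the bolus part, "Imaging time will be 15-20 minutes" (Section 4.2.2.1). For the infusion part, "Imaging time will be 3-15 minutes depending on mass size" (Section 4.2.2.2).
- **Sections 6.2 and 6.3.1:** AEs and SAEs are recorded through 30 days. These are recording rules and do not keep a nurse at the bedside.

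**The concern.** The conditional rule and the protocol's onset data do not fit together. Section 1.9 describes events starting up to 15 minutes after administration. Contrast is given again at the end of the session, and the last scan may be over in 3 minutes. A subject who feels well when the scan ends could then leave while the onset window is still open, with the written plan fully followed. If a reaction began after that, neither the nurse nor the epinephrine kept beside the scanner (Section 1.11) would be at hand. Most subjects have a single visit (Section 5.5), so no later study contact is planned at which it would be noticed promptly.

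What is at stake is prompt response to a late reaction. The estimates, tests and AE recording rules are not affected.

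**Working it through.** The plan states no figure for the length of post-imaging observation, so there is none to reproduce. The check compares the stated scan times with the stated onset window.

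**Inputs.** Bolus imaging 15-20 minutes (4.2.2.1). Infusion imaging 3-15 minutes (4.2.2.2). Infusion after boluses (5.3). Onset window 1-15 minutes (1.9). 25 subjects (7.1).

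**Assumption.** Observation of a subject without symptoms ends when imaging ends. This is inferred from the missing end time. Changeover time between the two parts is ignored; counting it would lengthen cover after the boluses.

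**Step 1, total imaging.** Shortest 15 + 3 = 18 minutes; longest 20 + 15 = 35 minutes.

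**Step 2, part of the 15-minute window left after imaging ends.** Formula: max(0, 15 - minutes of imaging after the reference point).

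| Clock starts at | Shortest scan | Longest scan |
|---|---|---|
| First bolus | max(0, 15 - 18) = 0 | max(0, 15 - 35) = 0 |
| Infusion start | 15 - 3 = 12 | 15 - 15 = 0 |

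The first bolus is fully covered. The gap belongs to the infusion, at 0 to 12 minutes. Counted from the end of contrast it could reach 15 minutes, but only on the further assumption that contrast runs until the last moment of imaging.

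**Step 3, which events the window describes.** Section 1.9 reports 26 serious events and 15 discontinuations, then turns to 11 other serious events. Since 26 - 15 = 11, the 1-15 minute window appears to describe the 15 discontinuation events.

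**Step 4, a ceiling on expected events, whatever their onset time.**
- Discontinuation events: 25 x 15/1716 = about 0.22.
- Allergic events at 1 in 10,000 (1.9): 25/10,000 = 0.0025.

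Only some of these would start after imaging. The documents give no rate for that share, so none is claimed.

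**Step 5, does the text close the gap elsewhere?** Sections 1.9 to 1.11, the study procedures, the events table and Section 6 were read for a post-imaging observation period for subjects without symptoms. None states one. The study schema (4.1) is not shown in the text available, so its content could not be checked.

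**The case against.** The strongest reply is that Section 1.10 records a deliberate choice. By the protocol's account, the old 30-minute mandate never covered ordinary patients and was withdrawn in 2011. The section says the higher-risk groups are excluded and adds symptom-triggered observation on top. In the events table, the CEUS study is also a visit column, so footnote 4 may mean nursing cover for the whole visit. On that reading the shortfall is only a missing end time.

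The risk argument is weaker than it first looks, too. Section 1.15 names hypersensitivity in patients without previous exposure as the greatest risk, but first exposure is the first bolus, and the session covers its 15-minute window. Section 1.9 describes the early events as moderate and usually self-limiting, and Section 1.6 says microbubbles clear within minutes.

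Most of this stands, and it keeps the point minor. Two things remain. First, on either reading no end time is written, so two nurses could release subjects at different times and both comply. Second, the trigger in Section 1.10 is worded to exclude a reaction that starts after imaging. The reliance on exclusions is also looser than it sounds: Section 1.10 says pulmonary hypertension is excluded, whereas criterion 3.2.3 excludes only the severe form (above 90 mmHg). Section 1.10 also cites studies showing no added risk in that group, so this is support for the point and not evidence of harm.

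A reader might infer that the plan breaches the label, or that every subject needs 30 minutes of observation. The documents support neither: as Section 1.10 reports it, the label asks for monitoring of all patients without fixing a duration, and a universal 30 minutes would be a preference.

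**Conclusion.** The point holds as a minor patient-safety gap. The 30-minute rule does not reach a reaction that begins after imaging, and routine observation has no stated end. If observation stops with imaging, 0 to 12 minutes of the 1-15 minute onset window, counted from infusion start, go unobserved. The 12-minute figure is the upper end, reached with a 3-minute infusion scan, and it depends on that reading of footnote 4. If the footnote means the whole visit, what remains is an unstated end time and a trigger that is too narrow.

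A reader might also infer that the safety data would be incomplete or biased. They would not be on this account: recording runs for 30 days, and no objective, endpoint or comparison depends on how long the nurse stays.

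**What to change.** Amend three places: Section 1.10, Section 4.2.2.2 and footnote 4 of Section 4.3.

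1. Require nurse observation with vital signs for every subject until 15 minutes after the last contrast administration, and state that routine observation ends then.
2. Apply the existing 30-minute rule to a reaction suspected during imaging or during that observation.

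Fifteen minutes matches the upper end of the onset window in Section 1.9.

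**Cost.** Up to 15 minutes more per session, so imaging plus observation takes at most 18 + 15 = 33 to 35 + 15 = 50 minutes, against 18 to 35 now. Over 25 subjects with one session each this is 25 x 15/60 = 6.25 nurse-hours, using nurses already present. A repeat or second-lesion session (Section 4.2.1) adds up to 15 minutes again. The change also needs a protocol amendment with IRB approval (Section 8.5). No endpoint, sample size or analysis changes.
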